## **7.5        Blinding**

This is an open-label study and randomized in Part 2. Designated personnel of the Sponsor will have access to treatment and/or randomization assignments prior to database lock to facilitate data analysis (see [Section 10.3.9](#)), as well as the bioanalytical analysis of PK and immunogenicity samples. A bioanalytical scientist in the Bioanalytical Sciences department of BMS Research & Development (or a designee in the external central bioanalytical laboratory) will have access to the randomized treatment assignments in order to minimize unnecessary bioanalytical analysis of samples.

## **7.6 Dosage Modification**

Intra-participant dose escalation/reduction of BMS-986218, nivolumab, or ipilimumab is not permitted in this study in order to allow better evaluation of the safety and efficacy at individual dose levels and schedules.

### **7.6.1 Dose-limiting Toxicities**

For the purpose of guiding dose escalation, DLTs will be defined based on the incidence, intensity, and duration of AEs that are possibly related to study treatment. The DLT period will be 8 weeks (56 days) in both the BMS-986218 Monotherapy Dose Escalation (Part 1A) and the Safety Evaluation of Combination Doses of BMS-986218 with Nivolumab (Part 1B). Any toxicities that occur beyond the DLT period will be accounted for in making final dose level decisions.

Participants receiving 2 doses of BMS-986218 and have completed or who discontinued due to a DLT in the 8-week DLT period will be considered as DLT-evaluable participants for BMS-986218 monotherapy. Participants receiving either 2 doses each of BMS-986218 and nivolumab, or participants who discontinued due to a DLT in the 8-week combination treatment DLT period, will be considered as DLT-evaluable participants for combination treatment. Participants who withdraw from the study during the DLT evaluation period or have received less than 2 doses for reasons other than a DLT in both monotherapy and combination therapy will not be considered as DLT-evaluable participants and may be replaced with a new participant at the same dose level. Participants who have received 2 doses and withdraw from the study during the last week of the DLT evaluation period for reasons other than a DLT in both monotherapy and combination therapy may be considered as DLT-evaluable. Participants who are dose delayed during the DLT evaluation period for reasons other than a DLT in both monotherapy and combination therapy could be considered as DLT-evaluable participants if they received 2 doses and completed at least 2 full cycles of therapy 4 weeks each, with a maximum of 12 weeks for the total duration, including delays.

For the purpose of participant management, any AE that meets DLT criteria, regardless of the cycle in which it occurs, will lead to discontinuation of study treatment. Participants who withdraw from the study during the 8-week DLT evaluation period for reasons other than a DLT may be replaced with a new participant at the same dose level. The incidence of DLT(s) during the 8-week DLT evaluation period will be used in dose escalation decisions and to define the MTD. AEs occurring after the DLT period will be considered for the purposes of defining the RP2D upon agreement between the Sponsor, Medical Monitor (or designee), and Investigators.

Participants experiencing a DLT will not be re-treated with study treatment and will enter the Safety Follow-up Period of the study. DLTs occurring after the 8-week DLT observation period will be accounted for in determining the dose levels for expansion.

AEs will be graded according to the NCI CTCAE v4.03.

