**Table 2-3: On-Treatment - Schedule of Activities for Q2W Dosing Schedules in BMS-986218 Monotherapy Escalation (Part 1A)**

Procedure	Cycle 1 (28 Days in Length) (Visit Window ± 2 Days, except for C1D1)				Cycle 2 (28 Days in Length) (Visit Window ± 2 Days)				Cycles 3 and Beyond (Each Cycle 28 Days in Length) (Visit Window ± 2 Days)	EOT a,b	Notes		
	DLT Period is Cycles 1 and 2												
	D1	D8	D15	D22	D1	D8	D15	D22	D1 & D15				
Safety Assessments													
ECOG Performance Status	X		X		X		X		X	X			
PE	X		X		X		X		X	X			
Symptom Directed PE		X		X		X		X					
Weight	X		X		X		X		X	X			
Vital Signs	X	X	X	X	X	X	X	X	X	X	
For BMS-986218, vital signs will be obtained within 30 minutes before the start of the infusion and then every 15 minutes (± 5 minutes) from the start of the infusion until 60 minutes after completion of the infusion for the first 3 doses of study treatment on C1D1, C1D15, and C2D1. For all doses after C2D1, vital signs and oxygen saturation are to be taken before the infusion and at the end of infusion.
 
If any vital sign is abnormal (based upon clinician assessment) at the final check, the participant must be observed further for a period of time, as clinically indicated.
		

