Weekly study visits will be performed for the first 8 weeks following the first dose of study treatment for the BMS-986218 Monotherapy Escalation (Part 1A), Safety Evaluation of Combination Doses of BMS-986218 with Nivolumab (Part 1B), the Randomized BMS-986218 Monotherapy Cohort Expansion in Cutaneous Melanoma (Part 2A), the Randomized BMS-986218 Monotherapy Cohort Expansion (Part 2B), the BMS-986218 Combination Therapy Cohort Expansion in NSCLC (Part 2C) and the BMS-986218 Combination Therapy Cohort Expansion in microsatellite stable colorectal cancer (MSS CRC) (Part 2D) followed by study visits Q4W thereafter. During Cycle 1 and Cycle 3 of the treatment period, additional study visits to collect samples for intensive PK, ADA, and cytokine assessments are required. See [Section 9.5](#) for further details.

In the BMS-986218 Monotherapy Escalation (Part 1A), the Randomized BMS-986218 Monotherapy Cohort Expansion in Cutaneous Melanoma (Part 2A), and the Randomized BMS-986218 Monotherapy Cohort Expansion (Part 2B), BMS-986218 will be administered Q4W. An alternative BMS-986218 dosing schedule of Q2W (with dosing on Day 1 and Day 15 of each 28-day cycle) will also be explored for monotherapy escalation using data obtained from the Q4W schedule. BMS-986218 will be infused over 30 minutes, except in the low-dose cohorts where infusion times may be shorter. BMS-986218 will require a 60-minute observation period following the completion of the infusion for the first 3 doses for each participant. Ipilimumab will be administered Q3W and will be infused over 30 minutes.

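### The 2-dose minimum for DLT-evaluability is all of the planned Q4W dosing in the 8-week window but only half of the planned Q2W dosing, so the Q2W DLT rate can be biased downward

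*Combined protocol and SAP*

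**What the plan says.** Section 7.6.1 sets one DLT window of 56 days for Part 1A and one monotherapy evaluability rule. It counts "Participants receiving 2 doses of BMS-986218 and have completed or who discontinued due to a DLT in the 8-week DLT period". The only exclusion based on exposure is for those who "have received less than 2 doses for reasons other than a DLT in both monotherapy and combination therapy".

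Two further clauses in the same section repeat the figure of two doses:
- Late withdrawal: "Participants who have received 2 doses and withdraw from the study during the last week of the DLT evaluation period" for a non-DLT reason may be counted.
- Dose delay: participants delayed for a non-DLT reason "could be considered as DLT-evaluable participants if they received 2 doses and completed at least 2 full cycles of therapy", within a 12-week limit.

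The Q2W schedule is described in Section 5.1.2 as "with dosing on Day 1 and Day 15 of each 28-day cycle", and the Q2W schedule of activities (Table 2-3) states "DLT Period is Cycles 1 and 2". No section gives a dose minimum specific to Q2W.

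**The concern.** On Q4W the rule asks for every scheduled dose in the window. Carried over unchanged to Q2W, it is met at half the scheduled doses. Doses are often missed because of toxicity that falls short of a DLT: Section 7.6.3 withholds treatment for Grade 2 diarrhea, for example, whereas the gastrointestinal DLT criteria in Section 7.6.1.1 start at Grade 3 for diarrhea. Under-exposed participants scored as having no DLT therefore pull the Q2W rate in one direction, towards apparent tolerability.

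Cohorts are small. Section 5.1.2.3 plans about 3 participants per dose level and allows a tolerability assessment once 2 evaluable participants have completed the window, so one under-exposed participant can be half the evidence. What is at stake is the Q2W tolerability finding and, through Section 5.1.2.1, any further Q2W dose in the PD cohort that is justified by it.

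**Working it through.** **1. Planned doses in the window.** Inputs: 56-day window (Section 7.6.1); dosing every 28 days, or on Days 1 and 15 of each 28-day cycle (Section 5.1.2).
- Q4W: 56/28 = 2 doses, so a minimum of 2 is 2/2 = 100%.
- Q2W: 56/14 = 4 doses, so a minimum of 2 is 2/4 = 50%.

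**2. The count that the rule governs.** Appendix 11, Section 3.1 allows at most 12 participants per dose level. Six Q2W levels give 6 × 12 = 72, the Q2W cap in Sections 5.1.2.1 and 5.2. Nine Q4W levels give 9 × 12 = 108, also as stated. A schedule-specific minimum leaves the 72 unchanged and alters only who counts towards it.

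**3. Exposure, not just dose count.** Assumed model: one compartment, bolus doses, half-life 15 days (the projection in Section 5.5.2.1), so k = ln 2/15. A dose given t days after the first contributes A(t) = 1 − exp(−k(56 − t)) to the 56-day AUC, in relative units.
- A(0) = 0.925, A(14) = 0.856, A(28) = 0.726, A(42) = 0.476; the sum for four doses is 2.983.
- Days 1 and 15 only: (0.925 + 0.856)/2.983 = 0.60.
- Days 1 and 29 only: (0.925 + 0.726)/2.983 = 0.55.
- Days 1 and 43 only: (0.925 + 0.476)/2.983 = 0.47.
- With half-lives of 10 and 20 days, the Day 1 and 15 pattern gives 0.57 and 0.62; the Day 1 and 43 pattern stays at 0.47.

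**4. Illustration on the plan's prior curve.** Appendix 11, Section 3.2 gives prior means of −0.619 for log α and −0.304 for log β, with a reference dose of 150 mg. The plug-in curve is p(d) = expit(−0.619 + exp(−0.304) × ln(d/150)). Assumption: risk follows total dose per 28 days, so 75 mg Q2W is entered as 150 mg.
- Full exposure: p(150) = 0.350, which reproduces the 0.35 printed in Section 3.3.
- Half: p(75) = 0.244. At 60%: p(90) = 0.270. At 47%: p(70.5) = 0.236.
- One of 6 half-exposed: (5 × 0.350 + 0.244)/6 = 0.332.
- Two of 6 half-exposed: (4 × 0.350 + 2 × 0.244)/6 = 0.315 (0.3147 before rounding the inputs), so about 0.31.
- All 6 under-exposed: 0.24 to 0.27.

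**5. Sensitivity to the model.** A different assumption, not in the documents, makes the DLT hazard proportional to exposure. A full-exposure rate of 0.33 then becomes 1 − 0.67^0.5 = 0.181 at half exposure. The chance of seeing at most 1 DLT in 6 is 0.36 with full exposure, 0.46 with 2 of 6 half-exposed, and 0.70 with all 6 half-exposed. The direction agrees with step 4.

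**The case against.** A reader might infer that any Q2W participant whose third and fourth doses are withheld for toxicity stays evaluable. The documents do not support that. Section 7.1.1 treats missed dosing visits as postponed rather than omitted, so withholding brings the dose-delay clause into play. That clause asks for two full cycles as well as two doses, and two full Q2W cycles can be read as four doses. It is also discretionary. Withdrawal before the last week already makes a participant non-evaluable and replaceable, and many treatment-related stops would themselves be DLTs under Sections 7.6.1.1 to 7.6.1.5.

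This narrows the gap without closing it. Section 8.1 keeps participants who ask to stop treatment in follow-up, so a permanent non-DLT stop after dose 2 with follow-up to Day 56 meets the main rule as written. The last-week clause can admit others. In the delay clause, two doses and two full cycles point to different minimums on Q2W.

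The second objection is reach. Q2W doses are guided by Q4W-equivalent doses that have cleared safety, up to the Q4W MTD equivalent (Section 5.1.2.1). A PD-cohort dose may qualify through the Q4W-equivalent route instead. Dose decisions also weigh data from all treated participants, including later toxicities (Section 7.6.1; Appendix 11, Section 3.1). All of this stands, and it bounds the consequence.

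Third, excluding under-exposed participants is itself informative, since it removes people prone to toxicity. That is right, and the fix has to allow for it.

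**Conclusion.** The evaluability rule does not carry over to Q2W: it demands 100% of planned doses on Q4W and 50% on Q2W, and no Q2W rule exists. This part rests on the text alone. Participants who enter through the gap have about 47% to 60% of planned 56-day exposure, given the one-compartment model and the projected half-life, so the Q2W DLT rate can be biased downward.

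The size of the bias cannot be fixed from the documents, because they give no frequency of such participants. The fall from 0.35 to about 0.31 (2 of 6 half-exposed), or to 0.24 to 0.27 (all under-exposed), is an illustration. It uses a plug-in of prior means built for Q4W doses and assumes that risk follows total dose. It would be too strong to read it as showing that 75 mg Q2W will look in-target when its true rate exceeds 33%: with one of six half-exposed the apparent rate is 0.332, essentially at the limit.

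A reader might also infer that the Part 2 doses are affected. They are not reached by this point, because Table 5.5.2-1 has Part 2 receiving BMS-986218 on Q4W only. The effect falls on Q2W tolerability findings and on PD-cohort doses that rely on them. The change should be made because the rule is plainly mismatched to the schedule and cheap to correct.

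**What to change.** In Section 7.6.1, state the evaluability minimum by schedule, as a share of the doses planned in the 56-day window (2 for Q4W, 4 for Q2W). Apply it in the same terms in the main rule, the last-week-withdrawal clause and the dose-delay clause, so that the dose count and the full-cycle requirement no longer diverge on Q2W. Treat participants below the minimum for non-DLT reasons as not evaluable and replaceable, which the section already allows. Report their toxicities alongside the DLT rate in each dose-level review, because leaving them out is not neutral. The sponsor sets the threshold and reconciles the passages.

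The cost is a short text change, possibly a few replacement participants within the existing cap of 72, and a re-check of past evaluability classifications at the Q2W levels that Section 3.2.1 lists as already given (20, 35 and 50 mg).

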### BMS-986218 Cohort Expansion - Combination Therapy in NSCLC (Part 2C)

In the BMS-986218 Combination Therapy Cohort Expansion (Part 2C), the preliminary efficacy and safety of BMS-986218 in combination with nivolumab will be investigated in participants whose NSCLC has progressed or relapsed after anti-PD-1/PD-L1 therapy. Participants must not have received prior anti-CTLA-4 therapy in the advanced or metastatic setting. Any selected BMS-986218 Part 2C dose will not exceed the highest Part 1B administered dose that has cleared safety, with a minimum of 6 evaluable participants for Safety Evaluation. More than one dose may be evaluated in Part 2C. The dose(s) of BMS-986218 selected for Part 2C will be based on the totality of available safety, PK, and pharmacodynamic data from Part 1 and Part 2. The nivolumab dose found to be tolerable in Part 1B will be used in Part 2C. In Part 2C, participants will be treated Q4W for a maximum duration of 2 calendar years regardless of treatment delays.

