## **8.2 Discontinuation from the Study**

Participants who request to discontinue study treatment will remain in the study and must continue to be followed for protocol specified follow-up procedures. The only exception to this is when a participant specifically withdraws consent for any further contact with him/her or persons previously authorized by participant to provide this information.

- Participants should notify the Investigator of the decision to withdraw consent from future follow-up **in writing**, whenever possible.
- The withdrawal of consent should be explained in detail in the medical records by the Investigator, as to whether the withdrawal is from further treatment with study treatment only or also from study procedures and/or post treatment study follow-up, and entered on the appropriate CRF page.
- In the event that vital status (whether the participant is alive or dead) is being measured, publicly available information should be used to determine vital status only as appropriately directed in accordance with local law.
- If the participant withdraws consent for disclosure of future information, the Sponsor may retain and continue to use any data collected before such a withdrawal of consent.

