### 9.2.1 Time Period and Frequency for Collecting AE and SAE Information

The collection of non-serious AE information should begin at initiation of study treatment until 100 days after the discontinuation of study treatment administration or until the start of a new anti-neoplastic treatment (whichever occurs first), at the timepoints specified in the Schedule of Activities (see [Section 2](#)).

Following the participant's written consent to participate in the study, all SAEs, whether related to study treatment or not, must be collected, including those thought to be associated with protocol-specified procedures.

- All SAEs that occur during the screening period and within 100 days after discontinuation of dosing must be collected, except in cases where a study participant has started a new anti-neoplastic treatment. However, any SAE occurring after the start of a new anti-neoplastic treatment that is suspected to be related to study treatment by the Investigator should be reported as an SAE.
- The Investigator must report any SAE that occurs after these time periods and that is believed to be related to study treatment or protocol-specified procedure.

- Medical occurrences that begin before the start of study treatment but after obtaining informed consent will be recorded on the appropriate section of the CRF section.
- All SAEs will be recorded and reported to Sponsor or designee within 24 hours, as indicated in [Appendix 3](#).
- The Investigator will submit any updated SAE data to the Sponsor within 24 hours of this being available.
- All SAEs, and all AEs (SAEs and non-serious AEs) associated with confirmed or suspected SARS-CoV-2 infection must be collected from the date of the participant's written consent until 100 days following last dose of study treatment.
- With the exception of nonserious AEs related to SARS-CoV-2 infection, all nonserious AEs (not only those deemed to be treatment-related) should be collected from the time of first dose and continuously during the treatment period and for a minimum of 100 days following last dose of study treatment.

Investigators are not obligated to actively seek AEs or SAEs in former study participants. However, if the Investigator learns of any SAE, including a death, at any time after a participant has been discharged from the study and he/she considers the event reasonably related to the study treatment or study participation, then the Investigator must promptly notify the Sponsor.

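### Part 1B evaluability lacks the completed-observation condition that monotherapy has, so a few combination participants lost to observation between about Day 29 and Day 56 can count as full non-DLTs

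*Combined protocol and SAP*

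**What the plan says.** Section 7.6.1 gives both parts the same window: "The DLT period will be 8 weeks (56 days) in both the BMS-986218 Monotherapy Dose Escalation (Part 1A", and the sentence goes on to name Part 1B. It then defines evaluability twice.

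- Monotherapy: "Participants receiving 2 doses of BMS-986218 and have completed or who discontinued due to a DLT in the 8-week DLT period".
- Combination: "Participants receiving either 2 doses each of BMS-986218 and nivolumab, or participants who discontinued due to a DLT" in the same 8-week period.

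The first asks for completion; the second does not. The exclusion that follows applies to both parts. It names "Participants who withdraw from the study during the DLT evaluation period or have received less than 2 doses for reasons other than a DLT" and rules that such people do not count as evaluable and may be replaced. Two further provisions also apply to both parts. Someone with 2 doses who withdraws in the last week of the window may still count, and someone with delayed doses must have completed two full 4-week cycles.

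Other sections bear on the reading:

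- Section 8.2 separates stopping treatment from leaving the study: "Participants who request to discontinue study treatment will remain in the study".
- Section 5.1.3.1 keeps safety visits 30, 60 and 100 days after the last dose, even if new anticancer therapy starts, unless consent is withdrawn.
- Section 9.2.1 collects non-serious AEs for 100 days "or until the start of a new anti-neoplastic treatment (whichever occurs first"). A later bullet in the same section asks for at least 100 days without that cut-off.
- Section 5.1.2.3 lets a cohort decision proceed once at least 2 evaluable participants have completed 8 weeks. Section 10.1.2 plans 6 to 12 DLT-evaluable participants per combination dose.
- The Synopsis text for Part 2C caps the dose at the highest cleared in Part 1B, "with a minimum of 6 evaluable participants for Safety Evaluation". Section 5.1.2.4 repeats this for Parts 2C and 2D.

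**The concern.** With Q4W dosing the second dose of each drug falls on about Day 29, so the combination sentence can be met halfway through the window. The exclusion turns on withdrawal from the study. A participant who dies of disease on Day 40, or who starts another anticancer therapy then, has not withdrawn and has had 2 doses. Nothing in Section 7.6.1 removes that participant from the evaluable set, and the unobserved days are treated as days without toxicity.

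The error runs in one direction. It lowers the Part 1B DLT rate that feeds the overdose check and the model-recommended MTD, and it helps a dose reach the count of 6. It also does so in the setting where Section 3.3 says a higher incidence of immune-mediated events is possible. Section 5.1.2.2 allows extra Part 1B participants for discontinuations, with progression as the example, before the 8-week period is complete. That suggests such people were meant to be replaceable, but the definition does not say so.

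**Working it through.** **Plan figures first.** The Part 1B maximum is 84 DLT-evaluable participants (Appendix 11, Section 4.1). With 7 dose levels and at most 12 per level, 7 × 12 = 84; the protocol does not write this derivation out.

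The prior combination DLT rates in Appendix 11, Section 4.3 also reproduce. The inputs are means −1.421 and −1.041 for BMS-986218 with reference dose 150 mg, and −1.856 for nivolumab at its reference dose.

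- p(d) = expit(−1.421 + exp(−1.041) × ln(d/150)); q = expit(−1.856) = 0.135.
- Additive joint rate = 1 − (1 − p)(1 − q).
- Results for 7 to 200 mg: 0.201, 0.227, 0.249, 0.270, 0.285, 0.303, 0.318. Stated: 0.20, 0.23, 0.25, 0.27, 0.28, 0.30, 0.32.

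**Who is affected.** After dose 2 and before Day 56, without a DLT:

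| Event | Status under 7.6.1, Part 1B |
|---|---|
| Withdraws before the last week | Excluded, replaceable |
| Withdraws in the last week (at least 49 of 56 days) | May count |
| Stops treatment only, stays in follow-up | Counts, and is observed: first safety visit about Day 29 + 30 = 59, ± 7 days |
| Dies of disease, or otherwise ceases to be observed without withdrawing | Counts, not observed to Day 56 |
| Starts new anticancer therapy | Counts; visits continue, but non-serious AE collection may stop under one sentence of 9.2.1 |

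The last row matters because a DLT need not be serious: Section 7.6.1.1 includes Grade 2 colitis lasting more than 5 days.

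**How much of a window is lost.** The protocol gives no onset pattern. Assume constant hazard and a true 56-day rate of 33%. The rate captured by day t is 1 − 0.67^(t/56).

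- Day 28: 18.1%, a shortfall of about 15 points.
- Day 49: 29.6%, a shortfall of about 3 points. This is the most the documents allow for a withdrawal.

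**Effect on a count of six.** Let t = 0.33, let k of 6 be followed to Day 28 only, and let F be the share of DLTs starting by then, so s = 0.33F. Then

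P(at most 1 DLT) = (1−t)^(6−k)(1−s)^k + (6−k)t(1−t)^(5−k)(1−s)^k + k·s(1−s)^(k−1)(1−t)^(6−k).

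- k = 0: 0.358.
- k = 1: 0.391 (F = 0.7) to 0.435 (F = 0.3).
- k = 2: 0.426 (F = 0.7) to 0.522 (F = 0.3).

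**Effect on the overdose check.** I used the Appendix 11, Section 4.2 priors, including the gamma interaction (mean 1.1, SD 0.5), with nivolumab at its reference dose. The posterior came from importance sampling with 2,000,000 draws. The table gives P(DLT rate ≥ 33%) against the 35% limit.

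| DLTs / counted | At 70 mg, with 1/6 at 20 mg and this result at 40 mg | At 40 mg, with this result at 20 mg only |
|---|---|---|
| 2/4 | 0.363 | 0.388 |
| 2/5 | 0.318 | 0.331 |
| 2/6 | 0.278 | 0.282 |
| 3/6 | 0.427 | 0.461 |
| 4/6 | 0.592 | 0.661 |

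If two of six counted were not observed to Day 56, the fully observed data are 2/4 (over the limit), while the rule uses 2/6 (under it). If only one of six was not, the comparison is 2/5 with 2/6, and both are under. The result depends on the count: with five counted and one unobserved, the comparison is 2/4 with 2/5, which does cross.

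**Allowing for replacement.** Non-evaluable participants may be replaced, so 2/4 would become 2/6, 3/6 or 4/6. At an assumed 30% rate, both replacements are DLT-free with probability 0.7² = 0.49, which gives 2/6 and the same recommendation. With probability 0.51 the result is 3/6 or 4/6, over the limit in both examples.

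**The case against.** A reader might infer from the combination sentence that Part 1B runs on a four-week window, or that anyone watched for four weeks counts. The documents do not support that. The same section sets 56 days for both parts and excludes study withdrawals before the last week in both. Its last-week and dose-delay provisions would have no purpose for Part 1B if two doses alone sufficed. Section 5.1.2.3 requires two completed windows before a cohort decision. A third participant may be incomplete only if a DLT in that participant would not alter the recommendation.

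Nor does stopping treatment mean that observation stops. Section 5.1.3.1 keeps the safety visits, and after a last dose on Day 29 the first falls near the end of the window. Dose 3 is not due until about Day 57. Someone who stops in between has had every scheduled dose and is normally followed, and removing such people would delete valid non-events and bias the rate upward. With scans every 8 weeks (Table 2-2), much scan-detected progression also comes close to Day 56. Finally, the model is guidance: decisions use all available safety data, and toxicities after the window are considered too.

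All of this stands, and it narrows the point to death from disease, new therapy, or another loss of observation without withdrawal. It does not close that gap. The two-completed-windows rule does not reach the rest of the 6 to 12 participants per dose. Section 9.2.1 is internally inconsistent on whether non-serious AE collection continues after new therapy starts, and new therapy confounds attribution in any case.

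**Conclusion.** The two evaluability sentences are inconsistent and should be reconciled. Followed literally, Part 1B counts a small group of incompletely observed participants as full non-DLTs, and the resulting bias is always downward.

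The size is modest. With six counted, two such participants can carry a dose across the 35% overdose limit (0.363 to 0.278, or 0.388 to 0.282), and one does not. Allowing for replacement at a 30% rate, the corrected rule would change the model's recommendation in about half of those two-in-six cases. The documents give neither a frequency for these losses nor a DLT onset pattern, so the figures are illustrations under assumed data, constant hazard or the stated onset range. They are not an estimate of what will happen. They use the 35% limit of Appendix 11, Section 4; the worked example in Section 5 of that appendix refers to 30% for the combination, and against that value one in six would also cross (0.318 to 0.278, or 0.331 to 0.282). No figure stated in the plan is wrong on account of this point.

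**What to change.** In Section 7.6.1, reconcile the two definitions so that Part 1B evaluability means 2 doses of each drug and completed DLT observation over the 56-day period, or a DLT within it. Keep the existing last-week and dose-delay provisions. Add one sentence stating that death from disease or new anticancer therapy before Day 56 without a DLT makes the participant non-evaluable and replaceable. State also that a participant who only stops treatment after both scheduled doses, and is observed through Day 56, remains evaluable. The test is then observation, not treatment status.

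The cost is a clause and two sentences, plus possibly a few more replacements in Part 1B. The maximum of 84 already counts evaluable participants, so it does not change.
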